5.3.5.8 Deaths

All deaths that occur during the protocol-specified adverse event reporting period (see Section 5.3.1), regardless of relationship to study drug or [^{18}F]GTP1 or an amyloid radioligand, must be recorded on the Adverse Event eCRF and immediately reported to the Sponsor (see Section 5.4.2). This includes death attributed to progression of AD.

Death should be considered an outcome and not a distinct event. The event or condition that caused or contributed to the fatal outcome should be recorded as the single medical concept on the Adverse Event eCRF. Generally, only one such event should be reported. If the cause of death is unknown and cannot be ascertained at the time of reporting, "**unexplained death**" should be recorded on the Adverse Event eCRF. If the cause of death later becomes available (e.g., after autopsy), "unexplained death" should

be replaced by the established cause of death. The term "**sudden death**" should not be used unless combined with the presumed cause of death (e.g., "sudden cardiac death").

If the death is attributed to progression of AD, "Alzheimer's Disease progression" should be recorded on the Adverse Event eCRF.

Deaths that occur after the adverse event reporting period should be reported as described in Section 5.6.

5.3.5.9 Preexisting Medical Conditions

A preexisting medical condition is one that is present at the screening visit for this study. Such conditions should be recorded on the General Medical History and Baseline Conditions eCRF.

A preexisting medical condition should be recorded as an adverse event only if the frequency, severity, or character of the condition worsens during the study. When recording such events on the Adverse Event eCRF, it is important to convey the concept that the preexisting condition has changed by including applicable descriptors (e.g., "more frequent headaches").

5.3.5.10 Lack of Efficacy or Worsening of Alzheimer's Disease

Events that are clearly consistent with the expected pattern of progression of the underlying disease should not be recorded as adverse events. These data will be captured as efficacy assessment data only. In most cases, the expected pattern of progression will be based on decline in clinical efficacy measures. In rare cases, the determination of clinical progression will be based on symptomatic deterioration. However, every effort should be made to document progression through use of objective criteria. If there is any uncertainty as to whether an event is due to disease progression, it should be reported as an adverse event.

5.3.5.11 Hospitalization or Prolonged Hospitalization

Any adverse event that results in hospitalization (i.e., inpatient admission to a hospital) or prolonged hospitalization should be documented and reported as a serious adverse event (per the definition of serious adverse event in Section 5.2.2), except as outlined below.

An event that leads to hospitalization under the following circumstances should not be reported as an adverse event or a serious adverse event:

- Hospitalization for respite care

- Hospitalization for a preexisting condition, provided that all of the following criteria are met:

The hospitalization was planned prior to the study or was scheduled during the study when elective surgery became necessary because of the expected normal progression of the disease

The patient has not experienced an adverse event

An event that leads to hospitalization under the following circumstances is not considered to be a serious adverse event, but should be reported as an adverse event instead:

- Hospitalization that was necessary because of patient requirement for outpatient care outside of normal outpatient clinic operating hours

5.3.5.12 Adverse Events Associated with an Overdose or Error in Drug Administration

An overdose is the accidental or intentional use of a drug in an amount higher than the dose being studied. An overdose or incorrect administration of study treatment is not itself an adverse event, but it may result in an adverse event. All adverse events associated with an overdose or incorrect administration of study drug or [¹⁸F]GTP1 or an amyloid radioligand (if considered to be an IMP) should be recorded on the Adverse Event eCRF. If the associated adverse event fulfills seriousness criteria, the event should be reported to the Sponsor immediately (i.e., no more than 24 hours after learning of the event; see Section 5.4.2).

No safety data related to overdosing of MTAU9937A are available.

5.3.5.13 Clinical Outcome Assessment Data

Adverse event reports will not be derived from COA data by the Sponsor, and safety analyses will not be performed using COA data, except for the C-SSRS. However, if any COA responses suggestive of a possible adverse event are identified during site review of the COA data (including the C-SSRS), the investigator will determine whether the criteria for an adverse event have been met and, if so, will report the event on the Adverse Event eCRF.

5.4 IMMEDIATE REPORTING REQUIREMENTS FROM INVESTIGATOR TO SPONSOR

Certain events require immediate reporting to allow the Sponsor to take appropriate measures to address potential new risks in a clinical trial. The investigator must report such events to the Sponsor immediately; under no circumstances should reporting take place more than 24 hours after the investigator learns of the event. The following is a list of events that the investigator must report to the Sponsor within 24 hours after learning of the event, regardless of relationship to study drug or [¹⁸F]GTP1 or an amyloid radioligand:

- Serious adverse events (defined in Section 5.2.2; see Section 5.4.2 for details on reporting requirements)
- Adverse events of special interest (defined in Section 5.2.3; see Section 5.4.2 for details on reporting requirements)
- Pregnancies (see Section 5.4.3 for details on reporting requirements)

The investigator must report new significant follow-up information for these events to the Sponsor immediately (i.e., no more than 24 hours after becoming aware of the information). New significant information includes the following:

- New signs or symptoms or a change in the diagnosis
- Significant new diagnostic test results
- Change in causality based on new information
- Change in the event's outcome, including recovery
- Additional narrative information on the clinical course of the event

Investigators must also comply with local requirements for reporting serious adverse events to the local health authority and IRB/EC.

5.4.2 Reporting Requirements for Serious Adverse Events and Adverse Events of Special Interest

5.4.2.1 Events That Occur prior to Initiation of Study Drug or [¹⁸F]GTP1 or an amyloid radioligand

After informed consent has been obtained but prior to initiation of study drug or [¹⁸F]GTP1 or an amyloid radioligand, only serious adverse events caused by a protocol-mandated intervention should be reported. The paper Clinical Trial Serious Adverse Event/Adverse Event of Special Interest Reporting Form provided to investigators should be completed and submitted to the Sponsor or its designee immediately (i.e., no more than 24 hours after learning of the event), by scanning and emailing the form using the email address provided below:

Email address: *[contact]*

5.4.2.2 Events That Occur after Initiation of Study Drug or [¹⁸F]GTP1 or an Amyloid Radioligand

After initiation of study drug or [¹⁸F]GTP1 or an amyloid radioligand, serious adverse events and adverse events of special interest will be reported until 12 weeks after the last dose of study drug or 4 days after the last dose of [¹⁸F]GTP1 or an amyloid radioligand, whichever is longer. Investigators should record all case details that can be gathered immediately (i.e., within 24 hours after learning of the event) on the Adverse Event eCRF and submit the report via the electronic data capture (EDC) system. A report will be generated and sent to Safety Risk Management by the EDC system.

In the event that the EDC system is unavailable, the paper Clinical Trial Serious Adverse Event/Adverse Event of Special Interest Reporting Form provided to investigators should be completed and submitted to the Sponsor or its designee immediately (i.e., no more than 24 hours after learning of the event), by scanning and emailing the form using the email address provided in Section 5.4.2.1. Once the EDC system is available, all information will need to be entered and submitted via the EDC system.

Instructions for reporting serious adverse events that occur > 12 weeks after the last dose of study treatment are provided in Section 5.6.

5.4.3 Reporting Requirements for Pregnancies

5.4.3.1 Pregnancies in Female Patients

Female patients of childbearing potential will be instructed to immediately inform the investigator if they become pregnant during the study or within 9 weeks after the last dose of study drug or 4 days after the last dose of [¹⁸F]GTP1 or an amyloid radioligand, whichever is longer. A paper Clinical Trial Pregnancy Reporting Form should be completed and submitted to the Sponsor or its designee immediately (i.e., no more than 24 hours after learning of the pregnancy), by scanning and emailing the form using the email address provided in Section 5.4.2.1. Pregnancy should not be recorded on the Adverse Event eCRF. The investigator should discontinue study drug and counsel the patient, discussing the risks of the pregnancy and the possible effects on the fetus. Monitoring of the patient should continue until conclusion of the pregnancy. Any serious adverse events associated with the pregnancy (e.g., an event in the fetus, an event in the mother during or after the pregnancy, or a congenital anomaly/birth defect in the child) should be reported on the Adverse Event eCRF. In addition, the investigator will submit a paper Clinical Trial Pregnancy Reporting Form when updated information on the course and outcome of the pregnancy becomes available.

5.4.3.2 Pregnancies in Female Partners of Male Patients

Male patients will be instructed through the Informed Consent Form to immediately inform the investigator if their partner becomes pregnant during the study or within 9 weeks after the last dose of study drug or 4 days after the last dose of [¹⁸F]GTP1 or an amyloid radioligand, whichever is longer. A paper Clinical Trial Pregnancy Reporting Form should be completed and submitted to the Sponsor or its designee immediately (i.e., no more than 24 hours after learning of the pregnancy), by scanning and emailing the form using the email address provided in Section 5.4.2.1. Attempts should be made to collect and report details of the course and outcome of any pregnancy in the partner of a male patient exposed to study drug. The pregnant partner will need to sign an Authorization for Use and Disclosure of Pregnancy Health Information to allow for follow-up on her pregnancy. After the authorization has been signed, the investigator will submit a paper Clinical Trial Pregnancy Reporting Form when updated information on the course and outcome of the pregnancy becomes available. An investigator who is contacted by the male patient or his pregnant partner may provide information on the risks of the pregnancy and the possible effects on the fetus, to support an informed decision in cooperation with the treating physician and/or obstetrician.

5.4.3.3 Congenital Anomalies/Birth Defects and Abortions

Any congenital anomaly/birth defect in a child born to a female patient exposed to study drug or [¹⁸F]GTP1 or an amyloid radioligand or the female partner of a male patient exposed to study drug or [¹⁸F]GTP1 or an amyloid radioligand should be classified as a serious adverse event, recorded on the Adverse Event eCRF, and reported to the

Sponsor immediately (i.e., no more than 24 hours after learning of the event; see Section 5.4.2). Any abortion should be reported in the same fashion (as the Sponsor considers abortions to be medically significant).

5.5 FOLLOW-UP OF PATIENTS AFTER ADVERSE EVENTS

5.5.1 Investigator Follow-Up

The investigator should follow each adverse event until the event has resolved to baseline grade or better, the event is assessed as stable by the investigator, the patient is lost to follow-up, or the patient withdraws consent. Every effort should be made to follow all serious adverse events considered to be related to study drug or [¹⁸F]GTP1 or an amyloid radioligand or trial-related procedures until a final outcome can be reported.

During the study period, resolution of adverse events (with dates) should be documented on the Adverse Event eCRF and in the patient's medical record to facilitate source data verification.

All pregnancies reported during the study should be followed until pregnancy outcome.

5.5.2 Sponsor Follow Up

For serious adverse events, adverse events of special interest, and pregnancies, the Sponsor or a designee may follow up by telephone, fax, email, and/or a monitoring visit to obtain additional case details and outcome information (e.g., from hospital discharge summaries, consultant reports, autopsy reports) in order to perform an independent medical assessment of the reported case.

5.6 ADVERSE EVENTS THAT OCCUR AFTER THE ADVERSE EVENT REPORTING PERIOD

The Sponsor should be notified if the investigator becomes aware of any serious adverse event that occurs after the end of the adverse event reporting period (defined as 12 weeks after the last dose of study drug or 4 days after the last dose of [¹⁸F]GTP1 or an amyloid radioligand, whichever is longer), if the event is believed to be related to prior study drug or [¹⁸F]GTP1 or an amyloid radioligand treatment. *If a patient discontinues the study due to an adverse event after 12 weeks after the final dose of study drug or after 4 days after the final dose of [¹⁸F]GTP1 radioligand or an amyloid radioligand, whichever is longer, the adverse event(s) leading to study discontinuation should be reported.* These events should be reported through use of the Adverse Event eCRF. However, if the EDC system is not available, the investigator should report these events directly to the Sponsor or its designee, either by faxing or by scanning and emailing the paper Clinical Trial Serious Adverse Event/Adverse Event of Special Interest Reporting Form using the fax number or email address provided to investigators.

5.7 EXPEDITED REPORTING TO HEALTH AUTHORITIES, INVESTIGATORS, INSTITUTIONAL REVIEW BOARDS, AND ETHICS COMMITTEES

The Sponsor will promptly evaluate all serious adverse events and adverse events of special interest against cumulative product experience to identify and expeditiously communicate possible new safety findings to investigators, IRBs, ECs, and applicable health authorities based on applicable legislation.

To determine reporting requirements for single adverse event cases, the Sponsor will assess the expectedness of these events using the following reference document:

- MTAU9937A Investigator's Brochure
- GTP1 Investigator's Brochure
- Investigator's Brochure or Summary of Product Characteristics or US Package Insert for amyloid ligand used, depending on whether the amyloid ligand is considered to be an IMP in the local jurisdiction

The Sponsor will compare the severity of each event and the cumulative event frequency reported for the study with the severity and frequency reported in the applicable reference document.

Reporting requirements will also be based on the investigator's assessment of causality and seriousness, with allowance for upgrading by the Sponsor as needed.

An iDMC will monitor the incidence of the above-listed anticipated events during the study. An aggregate report of any clinically relevant imbalances that do not favor the test product will be submitted to health authorities.

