4.6 TREATMENT, PATIENT, STUDY, AND SITE DISCONTINUATION

4.6.1 Study Treatment Discontinuation

Patients must permanently discontinue study treatment if they experience any of the following:

- Any medical condition that the investigator or Sponsor determines may jeopardize the patient's safety if he or she continues to receive study treatment
- Investigator or Sponsor determines it is in the best interest of the patient
- Pregnancy

The primary reason for study treatment discontinuation should be documented on the appropriate eCRF. Patients who discontinue study treatment prematurely will not be replaced.

Patients will return to the clinic for a treatment discontinuation visit 12 weeks (± 7 days) after the last dose of study drug (see [Appendix 1](#) and [Appendix 2](#) for additional details).

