5.3.1 Adverse Event Reporting Period

Investigators will seek information on adverse events at each patient contact. All adverse events, whether reported by the patient or noted by study personnel, will be recorded in the patient's medical record and on the Adverse Event eCRF.

After informed consent has been obtained but prior to initiation of study drug (MTAU9937A or placebo) or [¹⁸F]GTP1 or an amyloid radioligand, only serious adverse events caused by a protocol-mandated intervention (e.g., invasive procedures such as biopsies, discontinuation of medications) should be reported (see Section 5.4.2 for instructions for reporting serious adverse events).

After initiation of study drug or [¹⁸F]GTP1 or an amyloid radioligand, all adverse events will be reported until 12 weeks after the last dose of study drug or 4 days after the last dose of [¹⁸F]GTP1 or an amyloid radioligand, whichever is longer.

Instructions for reporting adverse events that occur after the adverse event reporting period are provided in Section 5.6.

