Appendix 1 Schedule of Activities (cont.)

Assessment	Screening Days –56 to –1 ⁱⁱ	Baseline ^a	Double-Blind Treatment Period																			Unplanned Visit ^b	Tx Completion ^f	Tx D/C ^c			
			1 ^a	3 ^d	5 ^d	9	13	17	21	25	29	33	37	41	45	49	53	57	61	65	69				73		
Week																											
Dose			1	2	3	4	5	6	7	8	9	10	11	12	13	14	15	16	17	18	19						
LP for CSF sample for PK and biomarkers ^{ff}	x	x														x								x		x ⁱ	
Concomitant medications ^{gg}	x ^{hh}	x	x	x	x	x	x	x	x	x	x	x	x	x	x	x	x	x	x	x	x	x	x	x	x	x ^{hh}	x ^{hh}
Adverse events ^{hh}	x ^{hh}	x	x	x	x	x	x	x	x	x	x	x	x	x	x	x	x	x	x	x	x	x	x	x	x	x ^{hh}	x ^{hh}

[¹⁸F]GTP1 = fluorine-18 Genentech tau probe 1; AD=Alzheimer’s disease; ADA=anti-drug antibody; ADAS-Cog=Alzheimer’s Disease Assessment Scale–Cognitive Subscale; ADCS-ADL=Alzheimer’s Disease Cooperative Study Group–Activities of Daily Living Inventory; CaGI-Alz = Caregiver Global Impression of Change Scales for Alzheimer’s disease; C-SSRS=Columbia-Suicide Severity Rating Scale; CDR=Clinical Dementia Rating; COA=clinical outcome assessment; CSF=cerebrospinal fluid; D/C=discontinuation; DVF = Diagnostic Verification Form; eCRF=electronic Case Report Form; HbA_{1c}=glycosylated hemoglobin; HBsAg= hepatitis B surface antigen; HCV= hepatitis C virus; iADL=Instrumental Activity of Daily Living; LP=lumbar puncture; MMSE=Min-Mental State Examination; MRI=magnetic resonance imaging; OLE=open-label extension; PET=positron emission tomography; PK=pharmacokinetic; RBANS=Repeatable Battery for the Assessment of Neuropsychological Status; RUD=Resource Utilization in Dementia; SNP=single nucleotide polymorphism; TSH= thyroid-stimulating hormone; Tx=treatment; WGS=whole genome sequencing.

Notes: All postbaseline study visits must be scheduled in reference to the first dosing day (Week 1/Dose 1 visit). All activities/assessments in a given study visit must be performed within ±5 days of the scheduled visit, unless otherwise specified (e.g., [¹⁸F]GTP1 PET scans). On study drug administration visits that span multiple days, study drug administration must occur on the last day. On study drug administration days, all assessments must be performed prior to dosing, unless otherwise specified.

On study drug administration days, pre-infusion laboratory samples should be drawn 0–4 hours before the start of infusion, and post-infusion laboratory samples should be drawn 0–30 minutes after the end of infusion, unless otherwise specified.

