Appendix 1 Schedule of Activities (cont.)

- i Only perform assessment if discontinuation visit is ≥ 16 weeks after last assessment for this instrument or procedure. However, if the patient discontinues study drug because of an infusion-related reaction, concurrent ADA and PK samples will also be collected at 12 weeks after the last administration of study drug.
- j Includes respiratory rate, pulse rate, and systolic and diastolic blood pressure while the patient is in a seated position, and temperature. Record abnormalities observed at baseline on the General Medical History and Baseline Conditions eCRF. At subsequent visits, record new or worsened clinically significant abnormalities on the Adverse Event eCRF. On study drug treatment visits, vital signs should be collected 0–4 hours prior to infusion and 60–90 minutes after completion of infusion.
- k Vital signs should be assessed on the same day(s) that the [^{18}F]GTP1 PET scan and/or LP are performed. Vital signs should be assessed just prior to injection of [^{18}F]GTP1 or initiation of the LP procedure, but no earlier than 1 hour prior to injection of [^{18}F]GTP1 or initiation of the LP procedure. Vital signs should also be assessed just after injection of [^{18}F]GTP1 or conclusion of the LP procedure, but no later than 1 hour after injection of [^{18}F]GTP1 or conclusion of the LP procedure.
- l Includes evaluation of the head, eyes, ears, nose, and throat, and the cardiovascular, dermatological, respiratory, and gastrointestinal systems. In addition, the musculoskeletal and genitourinary systems should be examined as clinically indicated. Record abnormalities observed at baseline on the General Medical History and Baseline Conditions eCRF. At subsequent visits, record new or worsened clinically significant abnormalities on the Adverse Event eCRF.
- m Perform a limited, symptom-directed examination at specified timepoints or as clinically indicated. Record new or worsened clinically significant abnormalities on the Adverse Event eCRF.
- n If amyloid PET is used to confirm amyloid positive eligibility, an LP will not be performed as part of screening. If amyloid PET result suggests a patient is amyloid negative, an LP may be performed as part of screening to re-assess amyloid positivity eligibility on the basis of CSF.

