Appendix 1 Schedule of Activities (cont.)

- ^{aa} Serum PK samples should be taken 0–4 hours before the start of infusion and 1 hour (± 15 minutes), 2 hours (± 20 minutes), and 4 hours (± 30 minutes) after the end of infusion.
- ^{bb} Serum PK and blood biomarker samples should be taken 0–4 hours before the start of infusion and 0–30 minutes after the end of infusion.
- ^{cc} Not applicable for a site that has not been granted approval for blood collection for SNP.
- ^{dd} Not applicable for a site that has not been granted approval for WGS.
- ^{ee} Blood biomarker samples should be taken 0–4 hours before the start of infusion unless otherwise noted.
- ^{ff} When an LP is performed, it should be performed only once during either screening or the baseline visit, and may be used for assessment of amyloid positivity (if performed at screening) and/or for assessing tau or other biomarkers. If a [^{18}F]GTP1 PET scan is not performed at the baseline visit, an LP at the baseline visit is mandatory for collection of CSF (unless performed during screening) to enable the assessment of tau biomarkers. Follow-up LPs must also be performed at postbaseline visits if a [^{18}F]GTP1 PET scan is not performed at the baseline visit. If [^{18}F]GTP1 PET is performed at baseline and LP is performed at the screening or baseline visit, then follow-up LPs are optional.
- ^{gg} Medication (e.g., prescription drugs, over-the-counter drugs, vaccines, herbal or homeopathic remedies, nutritional supplements) used by a patient in addition to protocol-mandated treatment from 3 months prior to screening until the final study visit.

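### Section 5.6 gives no route to the sponsor for a late, non-fatal serious event attributed to a study procedure, although a lumbar puncture may be done just as reporting closes

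*Protocol*

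**What the plan says.** - **Reporting period.** Protocol Section 5.3.1: "all adverse events will be reported until 12 weeks after the last dose of study drug or 4 days after the last dose of" GTP1 or an amyloid radioligand, whichever is longer. Section 5.4.2.2 repeats this for serious events and events of special interest.
- **Discontinuation visit.** Section 4.6.1: "Patients will return to the clinic for a treatment discontinuation visit 12 weeks (± 7 days) after the last dose of study drug".
- **LP at that visit.** The Appendix 1 row "LP for CSF sample for PK and biomarkers" has an entry at treatment discontinuation, subject to footnote i: "Only perform assessment if discontinuation visit is ≥ 16 weeks after last assessment for this instrument or procedure". Footnote ff adds: "Follow-up LPs must also be performed at postbaseline visits if a" GTP1 scan was not done at baseline. If one was done, follow-up LPs are optional. Appendix 2 also marks an LP at its discontinuation visit, but its footnote w makes every open-label extension (OLE) LP optional.
- **After the period.** Section 5.6 has two routes. A serious event is notified "if the event is believed to be related to prior study drug" or a radioligand. Separately, events that lead to study discontinuation are reported, with no condition on cause.
- **Deaths.** Footnotes hh (Appendix 1) and y (Appendix 2) ask for all deaths after the period, whatever the cause. Section 5.3.5.8 refers late deaths to Section 5.6, which does not mention them.
- **Procedures elsewhere.** Section 5.2.1 counts events related to a protocol-mandated intervention as adverse events. Before the first dose of drug or tracer, Section 5.3.1 asks for "only serious adverse events caused by a protocol-mandated intervention". Section 5.5.1 asks that serious events related to drug, tracer or "trial-related procedures until a final outcome can be reported" be followed.

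**The concern.** The protocol recognises procedure-related harm in its definition of an adverse event, in the period before first dose, and in the follow-up duty. The rule for the time after the reporting period leaves it out. That would be a formality if no invasive procedure came near the end of the period, but for patients who stop treatment early an LP can fall on the day reporting closes, or up to a week later.

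At stake is whether the sponsor learns of a non-fatal serious complication, such as a bleed or an infection, of a procedure done for research. Followed to the letter, the plan would capture that event before the first dose and could miss it after the last visit. The primary endpoint and the treatment comparison are not affected.

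**Working it through.** The plan states no figure on this point to reproduce. The check is day arithmetic plus a comparison of clauses.

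**1. Reporting days left after an LP at the discontinuation visit**

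Inputs: visit at 84 ± 7 days after the last dose, so day 77 to 91 (Section 4.6.1); period ends at day 84, or 4 days after a tracer dose if later (Section 5.3.1).

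Without a tracer: 84 − visit day. With GTP1 on the visit day: max(84, visit day + 4) − visit day.

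| Visit day | No tracer | GTP1 the same day |
|---|---|---|
| 77 | 7 | 7 |
| 80 | 4 | 4 |
| 84 | 0 | 4 |
| 87 | −3 (already closed) | 4 |
| 91 | −7 (already closed) | 4 |

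Patients for whom the LP is mandatory had no baseline GTP1 scan. Later scans are optional for them (Appendix 1, footnote o), so they will normally be in the middle column.

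**2. How often the 16-week condition lets the LP go ahead**

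Take each double-blind dose week (1, 3, 5, then every 4 weeks from 9 to 69; 19 in all) as the last dose. The visit is at last dose + 12 weeks. The previous LP is the baseline one, or the Week 49 one if the last dose was at Week 49 or later (an assumption). Visits are taken on the target day.

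| Baseline LP | Last-dose weeks failing the condition | Met |
|---|---|---|
| Week 1 | 1, 3, 49 | 16 of 19 |
| 2 weeks earlier | 1, 49 | 17 of 19 |
| About 10 weeks earlier (screening) | 49 | 18 of 19 |

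Week 69 is the last planned dose and belongs to completers. Without it the counts are 15, 16 and 17 of 18. The condition therefore rarely removes the LP.

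**3. Who is affected**

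- Completers: the last double-blind LP is at Week 73, four weeks after the Week 69 dose, which leaves 12 − 4 = 8 weeks of full reporting.
- OLE completers: the Week 169 LP falls on a dosing visit, with 12 weeks of reporting to follow.
- Early discontinuers: the table in step 1 applies.

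**4. Number of mandatory LPs**

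SAP Section 4.4.5 gives roughly 85% with a baseline GTP1 scan, so 457 × 0.15 = 68.6, about 69 without one. With the 25% dropout assumed in Protocol Section 6.1: 69 × 0.25 ≈ 17.

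**5. Routes for a serious LP complication that starts after the period**

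| Event | Route to sponsor |
|---|---|
| Fatal | Yes: footnotes hh and y |
| Leads to study discontinuation | Yes: Section 5.6, second route |
| Judged related to drug or radioligand | Yes: Section 5.6, first route |
| Non-fatal, attributed to the LP, study not discontinued | None stated |

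Footnotes hh and y repeat the same drug-or-radioligand condition, so they do not fill the last row.

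**The case against.** A reader might infer three stronger things, and the documents support none of them.

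- *That Section 5.6 accepts only drug- or tracer-related events.* Its second route takes any adverse event leading to study discontinuation. That route may rarely help, since the schedules show no further visit after the discontinuation visit, but it exists.
- *That a late LP complication has no reporting route at all.* Deaths are covered by footnotes hh and y. Table 6 also presumes an event related unless another etiology is evident or the timing is implausible, so a late bleed or infection of unclear cause would go through the first route. The gap needs an event positively attributed to the LP. That can happen: Section 5.3.4 asks about causality for drug and radioligands only, so a recognised LP complication would properly be marked unrelated.
- *That an LP at this visit gets no adverse-event follow-up.* Up to 7 days of full reporting may remain, vital signs are taken after the LP (footnote k), and Section 5.5.1 covers follow-up of procedure-related serious events.

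Other points have weight. The overview in Section 3.1.1 names mandatory LPs at baseline, Week 49 and Week 73 only, so the mandatory status at discontinuation rests on the general wording of footnote ff. Investigators also have separate duties to health authorities and ethics committees (Section 5.4), though these do not reach the sponsor's safety data. Finally, nothing links the radioligands' 4-day tail to how invasive a procedure is, so the absence of such a tail for LP is not in itself an inconsistency.

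What remains is that the clause in 5.6 omits procedures, which Sections 5.2.1, 5.3.1 and 5.5.1 all cover.

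**Conclusion.** The gap is real but narrow. It concerns a non-fatal serious event, attributed to a study procedure, that starts after the reporting period and does not lead to study discontinuation. The schedule makes this possible because the discontinuation-visit LP leaves between 7 days and no days of reporting, or 4 to 7 days with a same-day GTP1 scan.

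Only early discontinuers are exposed. About 17 mandatory LPs is a ceiling at the planned dropout rate. It assumes that every dropout among the roughly 69 patients attends the visit, meets the 16-week condition and has the LP, and people who withdraw consent may do none of these. Optional LPs in scanned patients and in the OLE come on top and cannot be counted from the documents. The ceiling counts procedures. The documents give no complication rate or onset time, so the number of missed events cannot be estimated and may be below one.

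The change is still worth making: it is specific, concerns harm from a research procedure, and brings 5.6 into line with the protocol's own treatment of such harm.

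**What to change.** In Section 5.6, and in the matching sentences of footnote hh (Appendix 1) and footnote y (Appendix 2), extend the relatedness condition so that it covers study drug, a radioligand *or a protocol-mandated procedure*.

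In the same edit, reconcile Section 5.3.5.8 with Section 5.6, so that the section to which late deaths are referred states how they are reported, in agreement with the two footnotes.

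The cost is one phrase in three places and one sentence on deaths. No visit, procedure or analysis is added, and the extra event entry is negligible.
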